### **5.7.2 CYP2D6 Inhibitors**

[REDACTED] The dose chosen in the study is considered safe also for poor CYP2D6 metabolizers.

[REDACTED]. Drugs that are CYP2D6 inhibitors, including paroxetine, are therefore allowed. However, the investigator (or qualified designee) should be aware of the likelihood for a higher exposure in these patients when judging the need for dose de-escalation or withdrawal.

### **5.7.3 Medication that May Lower the Seizure Threshold**

[REDACTED] medications that lower the seizure threshold must be avoided, and if a patient should start such a medication during the course of the study, he or she must be withdrawn (see Section 7.7.2).

### **5.7.4 Medication That May Cause QTc Prolongation**

In addition to the currently disallowed concomitant medications in the protocol, patients on pridopidine should not be allowed to take the following medications known to have a

---

substantial increase on QT interval: antidepressants (citalopram and escitalopram); antipsychotics (haloperidol, pimozide, clozapine, sertindole, and ziprasidone); and lithium. If these drugs are required for management of the patient, pridopidine should be discontinued.

#### **5.7.5 General**

All medications other than the IMP and disallowed medications (prescriptions or over-the-counter medications) started prior to the study or started during the study, must be documented on the concomitant therapy form in the eCRF.

Patients should continue on any medications which are already being prescribed. As far as possible the doses of these medications should be maintained unchanged throughout the study, unless a clinically-indicated change is needed. New medications may be introduced when judged clinically necessary.

Treatment with any of the disallowed medications listed in the current Operations Manual should not be commenced at any point during the study. If this occurs, the patient must discontinue IMP.

Certain antipsychotic medications (see Protocol Section 5.7 and current Operations Manual for disallowed medications) are allowed.

Where a change in dose of an existing medication or introduction of a new medication, other than excluded medications as above, is unavoidable i.e. where it is essential for the appropriate clinical management of the patient, the patient should wherever possible complete the IMP and all study assessments as per the study protocol.

Any changes to an existing concomitant medication or any new medication started during the study should be recorded in the eCRF.

For any concomitant therapy given as a treatment for a new condition or a worsening of an existing condition, the condition must be documented on the AE Form of the eCRF.

As part of the additional implemented monitoring procedures, information regarding changes in use of benzodiazepines and antidepressants will be collected in inquiries about concomitant medication. Inquiries about changes in use of alcohol and drugs associated with substance abuse (legal or illicit) will also be conducted. The information collected as part of the safety monitoring, together with the C-SSRS and the abbreviated PBA-s, will be verified with the patient's caregiver, spouse, or other support person (where necessary).

#### **5.7.6 Other Non-Drug Concomitant Therapy**

Other therapy may be administered as considered appropriate by the patient's physician.

---

 In accordance with the American Psychiatric Associations 2003 Practice Guideline for the Assessment and Treatment of Patients with Suicidal Behaviors.

---

### 5.7.7 Warnings and Precautions

[REDACTED]

[REDACTED]

[REDACTED] patients with a prolonged QTcF interval (defined as a QTcF interval of >450 ms for both males and females), or other clinically significant heart conditions will be excluded from clinical studies.

[REDACTED]

No patients with epilepsy or a history of seizure(s) of unknown cause should be treated with pridopidine. Patients included in studies should be monitored carefully as to exaggerated central nervous system reactions which may be indicative of a higher likelihood of seizure activity.

[REDACTED] Patients with significant renal impairment (creatinine clearance <40 mL/min) should not be treated with pridopidine.

[REDACTED] Medication containing CYP2D6 substrates with a narrow safety margin, e.g. class I anti-arrhythmics and tricyclic antidepressants, must therefore not be used.

Full details of AEs observed in reported clinical studies with the IMP can be found in the current Investigator's Brochure.

### 5.7.8 Availability of IMP After the Study

The study will continue until the IMP has been authorized for marketing by the respective regulatory authorities, or until the study is discontinued for medical/scientific (risk-benefit) or commercial reasons. No further treatment is planned by the Sponsor after the end of the Open-HART study. Patients are advised to return to their primary physician for additional treatment.

## 6 STUDY METHODS AND ASSESSMENTS

Full details of the required conduct of the study and the schedule of assessments are provided in Section 1.3.

It is recommended that the same qualified and trained investigator (or qualified designee) performs the neurological assessments, if possible. If the investigator (or qualified designee) cannot perform the assessments at a visit, the substituting investigator (or qualified designee) should be appropriately accredited. Investigators (or qualified designees) were trained in motor rating using the UHDRS and other rating scales during the preceding HART and PRIDE-HD studies.

If necessary, other qualified and trained investigators (or qualified designees) can perform other assessments (e.g. cognitive). The information about all personnel that have direct patient contact and the trainings that each one has received must be clearly identified and appropriate regulatory information must be on file.

Mobile nurses will be trained on the conduct of all study assessments before study virtualization.

After the VTV, in order to ensure timely assessments and compliance with IMP, it is recommended that the maximum period between VTV and each subsequent visit are as follows:

VTV to RV1	30 days from VTV
VTV to TC 1	13 weeks ±14 days from VTV
VTV to Remote Visit 2	26 weeks ±14 days from VTV
VTV Visit to TC 2	39 weeks ±14 days from VTV
VTV Remote Visit 3	52 weeks ±14 days from VTV
VTV to TC 3	65 weeks ±14 days from VTV
VTV to Remote Visit 4	78 weeks ±14 days from VTV
VTV to TC 4	91 weeks ±14 days from VTV; subsequent visits are every 13 weeks ±14 days thereafter (in between remote visits)
VTV to Remote Visit 5	104 weeks ±14 days from VTV; subsequent visits are every 26 weeks ±14 days thereafter

The schedule continues going forward in this manner, with alternating TCs every 3 months and remote visits every 6 months until the patient is withdrawn or the study ends.

### **6.1 Assessment of Efficacy**

May be conducted as decided by Sponsor.

### **6.2 ECG Assessments**

A single resting 12-lead ECG will be performed at VTV and all remote visits by mobile nurses. ECGs will be collected using ECG devices and measures of the cardiac intervals and morphological assessment. Participants have to be resting, in a comfortable supine position and environment, at least 15 minutes before each ECG sampling time point through at least 10 minutes after the collection.

A prolonged QTc interval at the VTV (defined as a QTcF interval of >450 ms for both males and females), or other clinically significant heart conditions as judged by the investigator (or qualified designee) is a violation of exclusion criteria and the patient will not be eligible for participation in the study.

QTcF Formula to be used:  $QTcF = QT/\sqrt{RR}$

Any clinically significant abnormalities observed by the investigator (or qualified designee) must be reported as AEs.

**In instances where there is an increase in QT/QTcF of >500ms or 60ms over the VTV, a second ECG should be repeated after 10 minutes rest to confirm the finding.** Where confirmed, this should be reported and documented on the eCRF as an AE.

Patients with a QTcF interval of >500 ms or if an increase in the average QTcF value is >60 ms from the VTV should be discontinued from the IMP and may remain in the study off IMP. A follow-up ECG should be done in 4 weeks.

If the central ECG reading results match the above criterion, the patient should stop taking IMP and may remain in the study off IMP.

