#### 1.4 List of Abbreviations

AE	Adverse Event
bid	Twice Daily
CFR	Code of Federal Regulations
CI	Confidence Interval
C max	Maximum Concentration
CMSU	Clinical Materials Services Unit
CRO	Contract Research Organization
C-SSRS	Columbia-Suicide Severity Rating Scale
CTCC	Clinical Trials Coordination Center
CYP2D6	Cytochrome P450 2D6
D2R	Dopamine D2 Receptor
DSMB	Data Safety Monitoring Board
DSM-IV-TR	Diagnostic and Statistical Manual – Fourth Edition – Text Revision
DTP	Direct-to-patient
EC	Ethics Committee
ECG	Electrocardiogram
eCRF	Electronic Case Report Form
EDC	Electronic Data Capture
EM	Extensive Metabolizers
EOS	End of Study
EOT	End of Treatment
ET	Early Termination
FDA	Food and Drug Administration
F/U	Follow-up
GCP	Good Clinical Practice
HART	ACR16C009: A Multi-center, Randomized, Double-blind, Parallel-group Study Comparing Three Doses of ACR16 Versus Placebo for the Symptomatic Treatment of Huntington’s Disease. IND: 77,419.
HD	Huntington’s Disease
HDPE	High-density Polyethylene
HSG	Huntington Study Group
HTT	Huntingtin Gene
IB	Investigator’s Brochure
IC50	Half Maximal Inhibitory Concentration
ICF	Informed Consent Form
ICH	International Council on Harmonisation
ID	Identification
IMP	Investigational Medicinal Product
IND	Investigational New Drug
IRB	Institutional Review Board
IRT	Interactive Response Technology
MermaiHD	ACR16C008: A Multi-center, Multi-national, Randomized, Double-blind, Parallel-group Study Comparing ACR16 45 mg Once-daily or Twice-daily Versus Placebo for the Symptomatic Treatment of Huntington’s Disease – Randomized Phase. EudraCT: 2007-004988-22.
mMS	Modified Motor Score
mPPT	Modified Physical Performance Test
MTD	Maximal Tolerated Dose
PBA-s	Problem Behaviors Assessment – Short Form
PDF	Portable Document Format
PET	Positron Emission Tomography

PK	Pharmacokinetics
PM	Poor Metabolizers
PRIDE-HD	A Phase 2, Dose-finding, Randomized, Parallel-group, Double-Blind, Placebo-controlled Study, Evaluating the Safety and Efficacy of Pridopidine 45 mg, 67.5 mg, 90 mg, and 112.5 mg Twice-Daily Versus Placebo for Symptomatic Treatment in Patients with Huntington's Disease (TV7820-CNS-20002) EudraCT: 2013-001888-23; IND 77,419
qD	Once Daily
QTcF	QT Interval Corrected for Heart Rate using Fredericia's Formula
REB	Research Ethics Board
RV	Remote Visit
RV1	First remote visit
S1R	Sigma-1 Receptor
SAE	Serious Adverse Event
TC	Telephone Contact
TFC	Total Functional Capacity
UHDRS	Unified Huntington's Disease Rating Scale

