#### 4.5 Exclusion Criteria

- [Revision 1] Ongoing treatment with tetrabenazine or deutetrabenazine, seizure threshold lowering medications, or certain antipsychotics and antidepressants (see Protocol Section 5.7 and current Operations Manual for list of disallowed medications).
- [Revision 2] Newly instigated or changed treatment with neuroleptics/anti-psychotics.
- [Revision 3] Use of tricyclic antidepressants or class I & III antiarrhythmics at any time during the study period.
- [Revision 4] Any clinically significant, abnormal laboratory result, including clinically significant hepatic or renal impairment, or any ongoing AE that, in the opinion of the investigator (or qualified designee), affects the patient's suitability for the study or puts the patient at risk if he/she continues in the study.
- [Revision 5] A prolonged QTc interval at the RV1 (defined as a QTcF interval of >450 ms for both males and females using Fredericia's formula) or other clinically significant heart conditions as judged by the investigator (or qualified designee).
- [Revision 6] Severe intercurrent illness that, in the opinion of the investigator (or qualified designee), may put the patient at risk when continuing participation in the study.
- [Revision 7] Alcohol and/or drug abuse as defined by the Diagnostic and Statistical Manual - Fourth Edition - Text Revision criteria for substance abuse – this includes the illicit use of cannabis.
- Patients with AEs of suicidal ideation or attempt at any time in the past or as measured by a suicide ideation score of  $\geq 3$  on the Columbia-Suicide Severity Rating Scale (C-SSRS) (who answer "Yes" to questions 3, 4, and 5 in the scale suicidal ideation section), or a score of  $\geq 3$  on the Problem Behaviors Assessment – Short Form (PBA-s), or patients who answer "Yes" on any of the 5 C-SSRS Suicidal Behavior Items (actual attempt, interrupted attempt, aborted attempt, preparatory acts, or behavior), if an attempt or acts were performed at any time in the past, or patients who, in the opinion of the investigator (or qualified designee), present a risk of suicide.
- Patients with a known history of epilepsy or a history of febrile seizure(s) or seizure(s) of unknown cause.
- Females who are pregnant or lactating.

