#### **5.3.1 Dose Frequency Reduction**

In the event of tolerability problems, patients will be instructed to immediately contact their investigator (or qualified designee) to discuss their AEs. The investigator (or qualified designee) will assess whether or not the AEs could be related to IMP and severe enough to warrant a dose frequency reduction. The patients will be instructed to stop taking 1 of the 2 capsules of their daily dose. Arrangements for an USV at the earliest opportunity will be made (see Section 4.6.5). At this visit patients will be provided with instructions regarding the de-escalated dose frequency. Alternatively, patients may be temporarily off drug up to 60 days per year in the event of tolerability problems, as judged by the investigator (or qualified designee).

---

IMP re-introduction or dose frequency increase back to the previous dose frequency may be considered if the clinical monitor, investigator (or qualified designee), and the patient agree that this should be attempted. Alternatively, qd dosing may be maintained.

Patients should be advised that if tolerability problems continue then they should contact their investigator (or qualified designee) who may then withdraw them from IMP (see Section 7.7.2 for withdrawal procedures).

IMP must be reduced to 45 mg qd for the following events:

- Any QTcF increase >60 ms from the first remote visit
- QTcF  $\geq$ 480 ms and  $\leq$ 500 ms
- Creatinine clearance <60 mL/min and >40 mL/min

If an IMP must be reduced to 45 mg qd and the patient is not currently at a study visit arrangements for an USV at the earliest opportunity will be made (see Section 4.6.5). At this visit, patients will be provided with instructions regarding the de-escalated dose frequency.

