### 7.5. Electrocardiography

Shifts (normal and abnormal) from baseline to overall finding and each visit will be summarized using patient counts. For overall finding, the summary will use the worst postbaseline finding for the patient (the abnormal finding if there are both normal and abnormal findings). Summary statistics for ECG variables will be presented at baseline and each visit. Actual values and changes from baseline to each visit will be summarized using descriptive statistics.

The incidence of potentially clinically significant abnormal values for ECG variables will be summarized using descriptive statistics with the criterion specified below.

- QTcF values  $>450$  ms or  $>480$  ms or  $>500$  ms.
- QTcF change from baseline values  $>30$  or  $>60$ .
- PR change from baseline  $\geq 25\%$  and value  $>200$ .
- QRS change from baseline  $\geq 25\%$  and value  $>110$ .
- Heart rate value  $<60$  bpm or  $>100$  bpm.

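### Protocol 6.2, as supplied, prints a square-root (Bazett) formula under the label QTcF, while the rest of the protocol defines QTcF by Fridericia, and the SAP states no formula for the QTcF values it tabulates

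*Protocol*

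**What the plan says.** Protocol 6.2 (ECG Assessments) gives the only explicit QTc formula in either document: "QTcF Formula to be used: $QTcF = QT/\sqrt{RR". In the text supplied the radical carries no index, so it is a square root.

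Everywhere that the protocol names the correction method, it names Fridericia (spelled Fredericia):

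- Section 1.4 defines QTcF as "QT Interval Corrected for Heart Rate using Fredericia's Formula".
- Section 4.5 sets the entry exclusion, "defined as a QTcF interval of >450 ms for both males and females using Fredericia's formula". The synopsis in 1.1 repeats it.
- The abbreviations under the 1.3 schedule give the same definition.

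The quantity called QTcF is then used in several places:

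- **Entry, as restated in 6.2:** "A prolonged QTc interval at the VTV (defined as a QTcF interval of >450 ms for both males and females", with no method named in that sentence.
- **On-study rules:** "Patients with a QTcF interval of >500 ms or if an increase in the average QTcF value is >60 ms from the VTV" in 6.2, and "Any QTcF increase >60 ms from the first remote visit" in 5.3.1.
- **Analysis:** SAP 7.5 counts QTcF above 450, 480 and 500 ms, and "QTcF change from baseline values $>30$ or $>60".

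The SAP gives no QTcF formula, and its Introduction sends the reader to the protocol for operational aspects of the assessments. SAP 2.1 states that the SAP rests on Amendment 04 and that Amendment 05, the virtualization amendment, was issued but not implemented.

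**The concern.** Dividing QT by the square root of RR is Bazett's correction. Dividing by the cube root is Fridericia's. One label therefore covers two quantities, and the only operational formula is the one that disagrees with the named method.

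A fixed millisecond cut-off means different things under the two corrections once heart rate departs from 60 bpm. Changes in pulse during treatment would also register as QTc change. That matters here because long-term safety is a primary objective (protocol 3.1), protocol 2.3 refers to dose- and exposure-dependent QTc findings in PRIDE-HD, and 6.2 schedules a single ECG per visit, so one heart rate determines each recorded value. Neither document states which correction the ECG devices or the central reading apply, so a reader of the SAP 7.5 tables could not tell which quantity was tabulated.

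**Working it through.** The plan contains no worked figure to reproduce. The check is algebra on the two forms.

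**Inputs from the documents:** the square-root form (protocol 6.2); Fridericia as the named method (1.1, 1.3, 1.4, 4.5); cut-offs of 450 and 500 ms and changes of 30 and 60 ms (protocol 4.5, 5.3.1 and 6.2; SAP 7.5).

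**Assumptions, not in the documents:** RR in seconds, so RR = 60/HR; illustrative resting rates of 50 to 90 bpm; an illustrative Fridericia value of 420 ms. The unit is not stated, but milliseconds would not work. With QT 400 and RR 1000, the square root gives 12.6 and the cube root 40.0, neither comparable with a 450 ms limit.

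**Step 1, ratio of the two forms.** Let B = QT / RR^(1/2) be the printed form and F = QT / RR^(1/3) be Fridericia. Then B/F = RR^(-1/6) = (HR/60)^(1/6), which equals 1 only at 60 bpm.

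**Step 2, what the cut-offs become.** F = B / ratio and B = F × ratio.

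| HR (bpm) | RR (s) | B/F | F when B = 450 | B when F = 450 | F when B = 500 |
|---|---|---|---|---|---|
| 50 | 1.200 | 0.9701 | 463.9 | 436.5 | 515.4 |
| 60 | 1.000 | 1.0000 | 450.0 | 450.0 | 500.0 |
| 70 | 0.857 | 1.0260 | 438.6 | 461.7 | 487.3 |
| 80 | 0.750 | 1.0491 | 428.9 | 472.1 | 476.6 |
| 90 | 0.667 | 1.0699 | 420.6 | 481.5 | 467.3 |

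Above 60 bpm the printed form flags patients whose Fridericia value is below the limit. At 80 bpm this is the band from about 429 to 450 ms. Below 60 bpm it misses patients above the limit. At 50 bpm this is the band from 450 to about 464 ms.

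**Step 3, apparent change at a constant Fridericia value of 420 ms.** B = 420 × (HR/60)^(1/6).

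- 60 to 80 bpm: 420.0 to 440.6, an apparent rise of 20.6 ms. That is 20.6/30 = 69% of the SAP's lower change category and 20.6/60 = 34% of the upper one.
- 60 to 90 bpm: 420.0 to 449.4, an apparent rise of 29.4 ms (98% and 49%).
- 70 to 60 bpm: 430.9 to 420.0, an apparent fall of 10.9 ms.

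The sign follows the direction of the heart-rate change, so a true change could be masked as well as created.

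**Step 4, what cannot be computed.** The documents give no distribution of QT or heart rate and no device or central-reader formula. The number of ECGs or patients that would change category therefore cannot be derived.

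**The case against.** The strongest objection is that there may be no error on the page. The text was read from a PDF by program, and a small 3 on the radical is easily lost. The left-hand side is labelled QTcF and every named method is Fridericia, so a lost index is plausible. This stands as a condition. The supplied text cannot settle it, and the source page must be checked before 6.2 is called wrong.

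Second, a reader might infer that the 450 ms entry rule wrongly excluded some patients and wrongly admitted others. The documents do not support that. The exclusion criterion itself names Fridericia, and misclassification would occur only if QTcF were calculated from 6.2 or a device were set up from it. The virtual transition visit and first remote visit at which the rule applies belong to Amendment 05, which the SAP says was not implemented. On that account no patient was screened at either visit. The formula printed in Amendment 04 is not in the text supplied.

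Third, SAP 7.5 does not cite protocol 6.2, so nothing shows that an analysed value came from the printed formula. That also stands. But the SAP gives no formula of its own and refers readers to the protocol, so nothing shows that it did not. The objections limit the consequence. They leave open which correction the tabulated QTcF uses.

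**Conclusion.** As supplied, the protocol contradicts itself: 6.2 prints the Bazett form under a label that four other sections define as Fridericia. If the printed form were used, QTcF thresholds would shift with heart rate. A printed 450 ms corresponds to Fridericia values from about 464 ms at 50 bpm to 421 ms at 90 bpm, and a 20 bpm rise from 60 bpm would add about 21 ms of apparent change at Fridericia 420 ms.

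These sizes rest on RR in seconds and on assumed heart rates. They show sensitivity and do not estimate how many patients were affected. Because Amendment 05 was not implemented, the main concern is the analysed QTcF values in SAP 7.5, with entry at the virtual visits secondary. The 6.2 contradiction is conditional on the source page showing a square root. The absence of a stated formula in the SAP is not.

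**What to change.** 1. Check the radical in the source PDF of 6.2. If it carries an index 3, the 6.2 point falls and only steps 3 and 4 remain.
2. If it is a square root, reconcile 6.2 with the Fridericia definition used elsewhere, QT / RR^(1/3) with RR in seconds.
3. State that formula and the unit of RR in SAP 7.5.
4. Confirm which correction the ECG devices and the central reading used under the implemented amendment.
5. Where stored values used the square root, recompute them before the SAP 7.5 tables are run. This needs QT with RR or heart rate from the same tracing. Equivalently, divide the stored square-root value by (HR/60)^(1/6). SAP 7.5 lists heart rate among its ECG variables but does not mention QT or RR, so availability must be confirmed.

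The cost is one symbol in 6.2, one sentence in the SAP and one query to the ECG vendor. Recomputation arises only if step 4 shows that it is needed. No clinical threshold is changed.
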